Pre-diabetes and Type II diabetes involve an impaired post-receptor response to insulin that hinders the glucose uptake response after meal consumption.¹⁷⁻¹⁹ Chronic hyperglycemia and the resulting compensatory hyperinsulinemia promote a cohort of acute and chronic sequelae including cardiovascular disease, liver complications, central nervous system degeneration and hyperglycemic osmotic stress.²⁰⁻²³ Axulin is a natural health product consisting of a mixture of extracts from herbs and vegetables present in normal diets which was identified by screening more than 100,000 compounds and extracts in a patented cell-culture based assay system targeting the IRS proteins. In vitro, Axulin has marked effects on the IRS-2 branch of the insulin signaling cascade to enhance downstream insulin signaling. Axulin has been shown in animal models to increase glucose uptake in peripheral tissues and decrease circulating blood glucose and triglyceride concentrations. Regular supplementation of the diet with Axulin would be expected to reduce the incidence of associated pre-diabetic and diabetic complications, resulting in an increased quality of life for patients without resorting to current anti-diabetic prescription drugs such as metformin and others that may have substantial unwanted side effects in patients.

HYPOTHESES

Axulin will reduce postprandial glucose and insulin responses in a dose-dependent fashion in healthy subjects without diabetes. The reduction in glucose and insulin will be relatively greater in insulin-resistant than insulin-sensitive subjects.

OBJECTIVES

The primary objective of this study is to determine the dose of Axulin which will reduce the incremental area under the blood glucose response curve (AUC) elicited by 75g oral glucose in healthy subjects by $\geq 33\%$.

The secondary objectives are to determine the dose-response effects of Axulin on:

- blood glucose and serum insulin AUC
- % reduction of insulin AUC
- the blood glucose and serum insulin increments at 15, 30, 45, 60, 90 and 120min
- insulinogen index
- Matsuda insulin sensitivity index
- ISSI-2 index of beta-cell function
- incremental blood lipid response at 120min
- plasma triglyceride response
- plasma axulin response

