The other objectives are to determine whether the effects of Axulin on glucose, insulin and triglyceride responses differ in lean vs overweight subjects and to determine whether the effects of Axulin on postprandial responses are similar when administered in capsule versus tablet form.

SUBJECTS

Inclusion criteria

Subjects will be males or non-pregnant, non-lactating females aged 18-60 years who have no history of diabetes and are in good health. Lean subjects will have a BMI >18.5 and $<25.0\text{kg}/\text{m}^2$, overweight subjects will have a BMI ≥ 25.0 and $<35.0\text{kg}/\text{m}^2$. Subjects taking stable doses (for at least 4 weeks of signing the consent form) of the birth control pill, thyroxin replacement therapy, statins, fibrates, cholesterol absorption inhibitors, anti-hypertensive medications, aspirin, non-steroidal anti-inflammatories and/or mild anxiolytics or sedatives can be included.

Female subjects of child-bearing potential must, for the duration of the study, be using one of the following birth control methods: total abstinence, a hormonal birth control method (oral, injectable, transdermal, or intra-vaginal), intrauterine device, or confirmed successful vasectomy of partner.

Exclusion criteria

- Fasting serum glucose $>6.9\text{mmol}/\text{L}$ (124mg/dL)
- HbA1c $>6.4\%$
- Fasting serum triglycerides $>4.5\text{ mmol}/\text{L}$ (399 mg/dL)
- Fasting LDL cholesterol $>4.99\text{ mmol}/\text{L}$ (192 mg/dL)
- Blood pressure >149 systolic or >89 diastolic
- Serum creatinine, or aspartate- or alanine transaminases >1.2 times upper limit of normal
- White cell count, red blood cell count, hemoglobin or hematocrit outside normal range
- Hospitalization for surgery or a medical condition within 3 months of signing the consent form

- Use of any drug to treat diabetes
- Use of medications other than those listed above or the presence of any condition which might, in the opinion of [name], either: 1) make participation dangerous to the subject or to others, or 2) affect the results
- Allergy or sensitivity to tarragon, chromium, escarole, lettuce, microcrystalline cellulose, inulin, food colouring (FD&C Yellow#5 and Blue#1) or vegetable-based capsules (silicon dioxide, titanium dioxide, hydroxypropylmethylcellulose)

Number of subjects

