The primary endpoint is the % reduction in 2-hour incremental AUC for glucose. Using the t-distribution with 2-tailed $p<0.05$ and assuming an average CV of within-individual variation of 2-hour incremental AUC values of 25%, $n=20$ subjects (10 lean and 10 overweight) has 80% power to detect a 17% difference in AUC, 90% power to detect a difference of 19% and 99% power to detect a difference of 26%. Within each subject group ($n=10$) there is 80% power to detect a difference in AUC of 25%, and 80% power to detect a 33% difference between the responses of lean and overweight subjects. To allow for 10% dropout, we will recruit $n=11$ lean and $n=11$ overweight subjects.

Subject Recruitment

Participants will be recruited from the pool of participants at GI Laboratories who have indicated that they are willing to be contacted and asked if they wish to participate in new studies. If an insufficient number of subjects can be recruited, then a newspaper advertisement will be used to recruit new subjects.

Selection of participants

Participants willing to be considered will be invited to come to the research centre to have the study procedures explained to them and be given a copy of the consent form which they may either sign then, take away to sign at a later date, or decline to participate. Participants will be encouraged to ask any questions they may have and not to sign the consent form until all of their questions have been answered to their satisfaction. Those who consent to participate will come to the research centre for a pre-selection visit when subject eligibility will be determined. During this visit, the 10-14hr overnight fasted participants will complete a questionnaire (Appendix 1) to assess medical history, and lifestyle factors, have height, weight, waist circumference and blood pressure measured, and have a blood sample drawn for measurement of glucose, HbA1c, lipids, creatinine, AST, ALT and complete blood count. Females will have a pregnancy test.

PROCEDURES

The study will have a randomized block design with repeated measures. One block, which will be double-blinded, will test the effect of Axulin capsules; the other block, which will be open label, will test the effect of Axulin tablets. Within each participant, the order of the blocks will be randomized and within each block the order of the treatments will be randomized.

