24	Overweight	A	C	B	F	E	D
25	Overweight	B	C	A	E	F	D
26	Overweight	C	A	B	D	F	E

27	Overweight	B	C	A	F	D	E
28	Overweight	D	F	E	B	A	C
29	Overweight	D	E	F	C	B	A
30	Overweight	F	E	D	A	B	C
31	Overweight	A	C	B	E	F	D
32	Overweight	E	D	F	C	A	B

Instructions: please assign capsules to codes A, B or C, and tablets or empty bag to codes D, E or F. Place treatment assignments into a sealed opaque envelope and keep the envelope in an accessible location. Treatments are as follows:

BLOCK 1 (A, B or C)

- Placebo 1; 16 Placebo capsules
- 2g Axulin caps: 4 Placebo capsules plus 8 Axulin capsules
- 4g Axulin caps: 16 Axulin capsules

BLOCK 2 (D, E or F)

- empty bag
- 2g Axulin tablets: 2 Axulin tablets
- 4g Axulin tablets: 4 Axulin tablets

Biochemical Analysis

Finger-prick blood samples for glucose analysis will be placed in the refrigerator immediately after being obtained and at the end of the test placed in a -20°C freezer until analysis which will be performed within 5 days. Glucose analysis is done using an YSI model 2300 STAT analyzer (Yellow Springs, OH). The microvette tubes used to collect blood for insulin analysis will be centrifuged at 3622×g for 2 min and the serum transferred to labeled polypropylene tubes and stored at -20°C prior to analysis of insulin using the Human Insulin EIA Kit (Alpco Diagnostics). Venous blood samples will be stored at 4°C until the end of the study after which they will be centrifuged at ~1400×g for 10 min and the plasma removed and separated into 2×1ml aliquots; 1 for analysis of triglycerides at St. Michael's Hospital biochemistry laboratory and the other for measurement of the active ingredient in Axulin by liquid chromatography/mass spectrometry.

Statistical Analysis

Incremental areas under the blood glucose, insulin and triglyceride response curves (AUC), ignoring area below fasting, will be calculated. Blood glucose and insulin concentrations and AUC values will be analyzed using repeated measures ANOVA examining for the main effects of dose, form (tablets vs capsules) and subject group (lean vs overweight) and their interactions. After demonstration of significant heterogeneity, differences between individual means will be assessed using Tukey's test to adjust for multiple comparisons.

Informed Consent

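### The stated 80% power for a 33% lean-versus-overweight difference allows for no person-to-person variation in the Axulin effect, so it is unsupported.

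*Combined protocol and SAP*

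**What the plan says.** All power figures are in the Number of subjects section of the combined protocol and SAP. One measure of variability is given, introduced by "assuming an average CV of within-individual variation of 2-hour incremental AUC values of 25" per cent, with a two-sided 5% t-test. From it the plan states that n=20 "subjects (10 lean and 10 overweight) has 80% power to detect a 17% difference in AUC", that each group of 10 has 80% power for 25%, and that there is "80% power to detect a 33% difference between the responses of lean and overweight subjects".

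The same section states: "The primary endpoint is the % reduction in 2-hour incremental AUC for glucose". The Objectives list, after the primary and secondary objectives, the question "whether the effects of Axulin on glucose, insulin and triglyceride responses differ in lean vs overweight subjects". The Hypotheses section predicts: "The reduction in glucose and insulin will be relatively greater in insulin-resistant than insulin-sensitive subjects". The Statistical Analysis section plans a repeated measures ANOVA on "main effects of dose, form (tablets vs capsules) and subject group (lean vs overweight) and their interactions".

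No between-subject CV, no SD of the % reduction and no estimate of how far the Axulin effect varies between people is given anywhere in the document.

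**The concern.** Each subject is their own control for Axulin against 0 g, so a within-individual CV is a natural starting point for the pooled comparison. No subject is their own control for BMI group. To compare the effect in 10 lean people with the effect in 10 other, overweight people, the error term needs two parts: the measurement noise in each person's % reduction, and the true spread of % reductions among people in the same group. The plan's figure contains at most the first.

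The plan's own hypothesis makes a zero second part hard to assume. If the effect depends on insulin resistance, and insulin resistance varies within a BMI group (a reasonable assumption, though not stated), effects will vary within groups too.

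The group terms in the ANOVA are the only planned analysis bearing on that second hypothesis; none by measured insulin sensitivity is specified. A reader who takes the 80% at face value could give a non-significant group result more weight than it deserves.

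**Working it through.** **Inputs from the plan (Number of subjects).** Two-sided alpha 0.05, t-distribution, 10 per group, within-individual CV 25%, power 80%, difference 33%.

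**Step 1: reproduce the stated figure.** For a two-sample t-test with 18 degrees of freedom:

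detectable difference = (t0.975 + t0.80) × SD × sqrt(2/10) = (2.101 + 0.862) × SD × 0.447 = 1.325 × SD.

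With SD = 25 this is 33.1%, and noncentral-t power at 33% is 79.7%. The plan's figure is recovered with 25% as the entire SD. As a cross-check, a one-sample (paired) t-test with SD 25 gives 16.5% for n=20 and 24.9% for n=10, matching the stated 17% and 25%. The same 25 therefore serves as the SD of a within-person difference and as the full SD of a between-group comparison.

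**Step 2: add the missing component.** For a comparison of % reduction between groups:

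SD = sqrt(W² + B²),

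where W is the within-person SD of the contrast and B is the between-person SD of the true % reduction, both in percentage points. The plan gives no B; 10 to 25 points is an assumed range. With W = 25:

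| B (assumed) | SD | Detectable at 80% power | Power at 33% |
|---|---|---|---|
| 0 | 25.0 | 33.1% | 80% |
| 10 | 26.9 | 35.7% | 74% |
| 15 | 29.2 | 38.6% | 67% |
| 20 | 32.0 | 42.4% | 59% |
| 25 | 35.4 | 46.8% | 51% |

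**Step 3: check how far this depends on W.** The Treatments section lists two 0 g tests and four active tests per person. The power statement does not say which are contrasted. Treating 25% as a single-visit CV, with equal SD at every visit:

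- Two 0 g against two same-dose visits: W = 25 × sqrt(1/2 + 1/2) = 25.0, the table above.
- Two 0 g against four active visits: W = 25 × sqrt(1/2 + 1/4) = 21.7.
- One control against one active visit: W = 25 × sqrt(2) = 35.4.

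Detectable difference (1.325 × SD):

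| B (assumed) | Two vs four, W = 21.7 | One vs one, W = 35.4 |
|---|---|---|
| 0 | 28.7% | 46.8% |
| 10 | 31.6% | 48.7% |
| 15 | 34.9% | 50.9% |
| 20 | 39.1% | 53.8% |
| 25 | 43.8% | 57.4% |

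In the two-versus-four case, the total SD reaches 25, and the detectable difference 33%, at B = sqrt(25² − 21.65²) = sqrt(625 − 468.75) = 12.5 points.

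**The case against.** The strongest reply is that leaving out a variance term makes 33% too small only if 25 is otherwise the right within-person SD, and the design offers contrasts for which 25 is too large. With two 0 g against four active visits, an effect SD of 10 points still gives 31.6%. A second route points the same way: if the CV stays at 25% while AUC falls by 33%, the SD of % reduction for two against two visits is about 0.67 × 25 = 16.8 points, and B could reach roughly sqrt(625 − 16.8²) ≈ 18 points before 33% is exceeded. This stands as a limit on the claim. A reader might infer that 33% is certainly too optimistic; the documents do not support that, because they do not name the contrast. Equally, they do not adopt either favourable reading, and the single-visit reading is worse than 33% before any effect variation is added.

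A reader might also take responses to mean AUC level and bring in the spread of AUC between people, which could give much larger figures. That is not supported either. The endpoint is % reduction and the objective concerns the Axulin effect; a person's stable AUC level largely cancels in that measure.

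It is also fair that every value of B here is assumed, that the comparison sits under the other objectives, and that no passage says a null group result will be taken as absence of a difference.

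**Conclusion.** The point holds as a wrong variance component in a power statement. The arithmetic is correct for its input, so this is not a calculation slip. The input is a within-individual CV applied as the full SD to a comparison between different people, and the 80% power at 33% is therefore unsupported.

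The size cannot be settled from the documents. If the within-person contrast SD is 25 points, assumed effect SDs of 10/15/20/25 points give 36/39/42/47%, with power at 33% of 74/67/59/51%. This is one conditional scenario and should not be copied into the plan as the answer. Averaging two 0 g against four active visits gives 32% to 44% over the same range, and exceeds 33% once the effect SD is above about 12.5 points. One visit against one gives 47% with no effect variation and 49% to 57% with it.

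A reader might conclude that the trial is too small. That does not follow: the primary sample size does not rest on the group comparison, and this point does not challenge it.

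**What to change.** In the Number of subjects section:

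1. Define responses, in the lean-versus-overweight sentence, as each person's % reduction in 2-hour incremental glucose AUC.
2. Name the visits contrasted to obtain it.
3. Recompute the group figure with SD = sqrt(within-person contrast variance + between-person variance in % reduction), using the sponsor's own estimate or a stated assumed range.
4. Replace the unqualified 33% with the result and label the lean-versus-overweight comparison exploratory.

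The cost is a rewritten sentence or two, plus an estimate or stated assumption for the spread of effect. No extra subjects, visits or changes to the analysis are needed. The downside is a stated sensitivity that will probably look less favourable.

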Eligible participants will be instructed to maintain stable dietary and exercise habits and for the duration of the study, to avoid vigorous physical activity for 24hr before each visit and to and consume their normal dinner the night before each visit. At each visit current use of medications and natural health products participants will be reviewed with each participant and any changes will be discussed with the investigator. Female participants will be advised that if they become pregnant during the study they are to contact the investigators and discontinue their participation immediately.

Each subject will be studied on 6 separate days with at least a 3-day interval between tests. On each test day, subjects will come to GI Labs ([name]) in the morning after a 10-14h overnight fast. On each test occasion the subject will be weighed, and give fasting finger-prick and venous blood samples. Blood from a forearm vein will be collected into a 6ml EDTA tube (Vacutainer, BD Canada, Mississauga, ON). Finger-prick blood samples will be collected into 2 separate vials: one (2-3 drops blood into a fluoro-oxalate tube) for glucose analysis and the other (6-8 drops of blood into an 0.3ml Microvette with clot activator, Sarsted, Germany) for insulin. After the fasting sample the subject will take 12 capsules or 2 tablets with a drink of 250ml water. Subjects will rest for 3-10min and have their blood pressure measured; 40min after swallowing the first capsule or tablet a finger-prick blood sample (2-3 drops for glucose and 6-8 drops for insulin analysis) will be collected and then subjects will consume 82.5g dextrose (containing 75g anhydrous glucose) dissolved in 300ml water within 5min plus a drink of 150ml water within 10min of starting the glucose drink. Further finger-prick blood samples for glucose (2-3 drops) and insulin (6-8 drops) will be obtained at 15, 30, 45, 60, 90 and 120 min after starting to drink the glucose solution. Venous blood samples (7ml) will be collected after the 60 and 120 min finger-prick. During the test subjects will remain seated quietly except for trips to the washroom if necessary. After the last blood sample subjects will be offered a snack and be free to leave.

Treatments

The 6 treatments administered will consist of the following:

- 12 placebo capsules with 250ml water (0g Axulin)
- 250ml water alone (0g Axulin)

- 4 placebo and 8 Axulin capsules (2g Axulin)
- 16 Axulin capsules (4g Axulin)

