- 2 Axulin tablets (2g Axulin)
- 4 Axulin tablets (4g Axulin)

Each placebo capsule contains 250mg inulin, each identical-looking Axulin capsule contains 250mg Axulin. It is anticipated that Axulin will be sold in tablets because 1g can be compacted into a tablet without loss of biological activity, but, because Axulin is a low-density powder, only 400mg can be placed in a capsule of similar size. We will use capsules in this study because it is more economical to produce the relatively small number of identical-looking placebo capsules required as compared to producing placebo tablets. To obtain doses in 1g increments, we will use smaller capsules containing 250mg each. The rationale for including tablets in the study is that Axulin in tablet form might be more slowly bioavailable than when encapsulated; thus, it is

important to determine whether the effects of Axulin tablets on postprandial responses is similar to the same dose taken in capsules.

Blinding

The number of Placebo and Active Axulin capsules and tablets required for the study will be provided to GI Labs. A person not involved in any other aspect of the study will make up 6 small zip-lock plastic bags for each subject labelled with a subject number and visit number and containing the treatment for visits 1 through 6 (the bag for the water alone treatment will be empty). The treatments will be randomized as shown in Table 1. The order of the blocks and the order of the treatments within each block were randomized using the @rand() function of Excel with 2 blocks of 6 created for lean subjects and 2 blocks for overweight subjects; the 2 extra orders are for use in case of drop-outs so that at least n=20 subjects complete the study (see Table 1). The person labeling and filling the bags with the treatments will assign the treatments to the codes and place the treatment assignments in a sealed opaque envelope kept in an accessible location. The envelope will be opened only after the study has been completed and the database locked, or in case of emergency if required for participant safety.

Table 1: Randomization Scheme

ID	Group	Visit 1	Visit 2	Visit 3	Visit 4	Visit 5	Visit 6
1	Lean	A	B	C	E	D	F
2	Lean	B	C	A	E	F	D
3	Lean	F	D	E	C	A	B
4	Lean	B	A	C	F	E	D
5	Lean	D	E	F	A	C	B
6	Lean	D	F	E	C	B	A
7	Lean	F	D	E	A	C	B
8	Lean	C	B	A	D	E	F
9	Lean	D	F	E	B	C	A
10	Lean	C	A	B	E	D	F
11	Lean	B	A	C	E	F	D
12	Lean	F	E	D	A	B	C
21	Overweight	D	E	F	C	B	A
22	Overweight	F	D	E	B	A	C
23	Overweight	A	B	C	E	D	F

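### Capsule and tablet counts conflict in three places: the test-day sentence cannot deliver 4 g, and one arm of the blinded capsule block can be identified by counting

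*Combined protocol and SAP*

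**What the plan says.** Unit counts appear in three places in the combined protocol and SAP.

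- **PROCEDURES, test-day description:** "After the fasting sample the subject will take 12 capsules or 2 tablets with a drink of 250ml water". One count is given for capsules and one for tablets, whatever the dose.
- **Treatments:** the capsule arms are "12 placebo capsules with 250ml water (0g Axulin"), "4 placebo and 8 Axulin capsules (2g Axulin") and "16 Axulin capsules (4g Axulin"). The tablet arms are 2 tablets for 2 g and "4 Axulin tablets (4g Axulin").
- **Blinding, bag-filling instructions below Table 1:** placebo is now "Placebo 1; 16 Placebo capsules", the middle dose is "2g Axulin caps: 4 Placebo capsules plus 8 Axulin capsules", and the 4 g arm is again 16 active capsules. Tablet counts are 2 and 4, as under Treatments.

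On masking, PROCEDURES says: "One block, which will be double-blinded, will test the effect of Axulin capsules". The tablet block, which includes the water-alone visit, is open label. The safeguards described are capsules of identical appearance, bags made up by someone with no other part in the study, and a sealed envelope holding the key to the codes. Nothing conceals how many capsules a bag contains.

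**The concern.** Two separate things are at stake.

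**Dose.** The primary objective is to find the dose that lowers glucose AUC by at least 33%, and dose is a main effect in the planned ANOVA. If the test-day sentence is followed, both 4 g arms receive less than their label says, and by different amounts. That would mislabel the top dose and confound the capsule-versus-tablet comparison at that dose.

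**Blinding.** The capsule block is the only blinded, placebo-controlled part of the trial; the tablet arms are open label with water as their comparator. Matching appearance does not mask an arm whose bag holds a different number of capsules. The design makes this easier to notice, because every participant takes all three capsule treatments and can compare the counts.

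The cue can also spread. Codes A, B and C are each assigned to a treatment once for the whole study, and Table 1 gives the code for every participant and visit. Bags carry participant and visit numbers, so anyone who holds Table 1 and recognises one bag can locate that arm in every row.

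**Working it through.** **Inputs.** Active and placebo capsules are 250 mg each (Treatments). A tablet is 1 g (Treatments, consistent with 2 tablets for 2 g). Counts are those listed above.

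**Formulas.** Dose = active units × strength. Arm total = placebo capsules + active capsules.

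**Step 1: the stated doses reproduce.**
- 8 capsules × 0.25 g = 2 g; 16 capsules × 0.25 g = 4 g.
- 2 tablets × 1 g = 2 g; 4 tablets × 1 g = 4 g.

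The two lists agree with each other on every active dose and on the tablet counts.

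**Step 2: the test-day sentence.**
- 12 capsules × 0.25 g = 3 g at most, which is 3/4 = 75% of the 4 g dose.
- 2 tablets × 1 g = 2 g, which is 2/4 = 50% of the 4 g dose and the same as the 2 g tablet arm.

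Taken literally, the nominal 4 g capsule-versus-tablet comparison becomes 3 g against 2 g, and the two tablet arms no longer differ.

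**Step 3: capsule totals in the blinded block.**

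| Arm | Treatments | Bag-filling instructions | All bags at 16 |
|---|---|---|---|
| Placebo | 12 + 0 = 12 | 16 + 0 = 16 | 16 + 0 = 16 |
| 2 g | 4 + 8 = 12 | 4 + 8 = 12 | 8 + 8 = 16 |
| 4 g | 0 + 16 = 16 | 0 + 16 = 16 | 0 + 16 = 16 |
| Arm that stands out | 4 g | 2 g | none |

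(Each cell is placebo + active = total.)

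Under either current list, one arm differs from the other two by four capsules. Someone who knows the list identifies that arm with certainty and has a 1 in 2 chance of ordering the remaining two. With equal counts and no other cue, the chance of ordering all three correctly is 1/(3 × 2 × 1) = 1 in 6.

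**Step 4: the placebo.** Its content is not settled either: 12 × 0.25 g = 3 g of inulin by one list and 16 × 0.25 g = 4 g by the other.

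**Step 5: can the three statements be reconciled?** Swallowing exactly 12 capsules at every capsule visit would equalise the number taken, but it caps the dose at 3 g and leaves four capsules in any bag of 16. Giving the whole bag delivers 4 g but leaves totals of 12/12/16 or 16/12/16. No reading of the current text gives both a 4 g dose and equal counts.

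**The case against.** The best reply is that this is a drafting slip with little practical effect. The two places that define the treatments agree on all active doses, and bags are filled in advance for each participant and visit. The test-day sentence does not cover the water-alone visit, so it cannot be a complete dosing instruction. Under-dosing would require staff to leave part of a bag unused.

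On blinding, the bag-filling instructions are probably the operative list. Under them placebo and 4 g both hold 16 capsules, so the most important contrast is not separated by count. A participant who notices a different number still needs the list to know which dose it means. The primary endpoint is glucose measured by a laboratory analyser, which leaves little room for observer bias, and half the visits are open label by design.

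Much of this stands. The dosing failure is conditional on following the test-day sentence, and the loss of masking is confined to one arm. The likely bias in the primary endpoint is small, although the documents do not allow it to be quantified.

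The reply does not settle which instruction governs, and it does not give the block equal counts under either list. Adverse events are assessed at every visit, and the study physician judges their causality. The documents do not say whether that physician would see the bags, but those judgements are more exposed to knowledge of treatment than a glucose assay.

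**Conclusion.** The concern holds. As written, the protocol gives conflicting instructions for the study product, and its claim of double blinding fails under both treatment lists.

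- **Dose:** the test-day sentence allows at most 3 g by capsule or 2 g by tablet in arms labelled 4 g. This assumes that staff follow that sentence; if they give the whole bag, 4 g is delivered.
- **Blinding:** exactly one of the three capsule arms is identifiable by count, 4 g under Treatments or 2 g under the bag-filling instructions. This assumes that counts are visible, and no procedure says otherwise. Extending it to all participants also requires access to Table 1.
- **Tablets:** the conflict here affects dosing only, because that block is open label.

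This must be corrected before bags are filled, because it determines what participants receive and whether the only blinded comparison is in fact blinded.

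**What to change.** 1. Put 16 capsules in every capsule bag: placebo 16 placebo; 2 g arm 8 placebo plus 8 active; 4 g arm 16 active. Doses stay at 0, 2 and 4 g.
2. Use these counts identically under Treatments and in the bag-filling instructions below Table 1.
3. Replace the fixed count in the test-day procedure with an instruction to take the entire contents of that visit's bag. This also covers 2 or 4 tablets and the empty bag for water alone.

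**Cost.** Wording in three places, plus placebo capsules. Against the bag-filling list, the 2 g arm needs 8 − 4 = 4 more per participant, or 4 × 24 = 96 for the 24 rows of Table 1. Against the Treatments list, the placebo arm also needs 16 − 12 = 4 more, making 8 per participant, or 8 × 24 = 192. Every participant swallows 16 capsules at each of the three capsule visits, 48 in all, compared with 16 + 12 + 16 = 44 or 12 + 12 + 16 = 40 under the current lists. Sample size, visits and analysis are unchanged.

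### The planned form and form-by-dose terms mix formulation with a difference between inulin placebo and water, and the primary % reduction names neither of the two zero arms as its reference

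*Combined protocol and SAP*

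**What the plan says.** All references are to the combined protocol and SAP.

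- **Placebo content (Treatments).** "Each placebo capsule contains 250mg inulin, each identical-looking Axulin capsule contains 250mg Axulin".
- **Capsule arms.** Treatments lists the zero arm as "12 placebo capsules with 250ml water (0g Axulin"); the instructions under Table 1 give "Placebo 1; 16 Placebo capsules". The active arms there are "2g Axulin caps: 4 Placebo capsules plus 8 Axulin capsules" and "4g Axulin caps: 16 Axulin capsules".
- **Tablet block.** The zero arm is "250ml water alone (0g Axulin"), supplied as an empty bag. The active arms are 2 or 4 tablets with no placebo units.
- **Blinding (Procedures).** The capsule block is double-blind and the tablet block is open label.
- **Objectives.** The primary objective is the dose that lowers the glucose incremental AUC by at least 33%. A further objective is to determine "whether the effects of Axulin on postprandial responses are similar when administered in capsule versus tablet form".
- **Primary endpoint (Number of subjects).** It is the % reduction in 2-hour glucose incremental AUC. No reference arm is given.
- **Statistical Analysis.** The plan is a repeated measures ANOVA "examining for the main effects of dose, form (tablets vs capsules) and subject group", with interactions. Tukey comparisons of individual means follow only if significant heterogeneity is found. No individual contrast is named.

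**The concern.** In the capsule block Axulin displaces inulin, so the dose comparison there also runs from most inulin to none. The tablet block has no such gradient. If the inulin placebo changes the glucose response at all, the planned form and form-by-dose terms will pick that up and it will be read as a property of the formulation. The documents do not say that 3 g or 4 g of inulin leaves glucose or insulin unchanged.

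The primary objective is a threshold. With two Axulin-free arms and no stated reference, the same 4 g capsule data can give two different % reductions. Unless the choice is fixed beforehand, the more favourable one could be chosen after unblinding.

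**Working it through.** **1. Inulin per treatment** (placebo capsules × 0.25 g)

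| Axulin dose | Capsule block | Tablet block |
|---|---|---|
| 0 g | 12 × 0.25 = 3 g, or 16 × 0.25 = 4 g | 0 g |
| 2 g | 4 × 0.25 = 1 g | 0 g |
| 4 g | 0 g | 0 g |

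The tablet column assumes inulin-free tablets; tablet excipients are not stated. Within the capsule block the correlation of inulin with Axulin dose is -0.98 (12 placebo capsules) or -0.96 (16).

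**2. What each term absorbs.** Let inulin change the AUC by b per gram, assumed linear. The first figure is for 12 placebo capsules, the second for 16.

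- Form main effect: (3+1+0)/3 - 0 = +1.33b; (4+1+0)/3 - 0 = +1.67b.
- Form-by-dose, 4 g vs 0 g: (0-3) - (0-0) = -3b; -4b.
- Form-by-dose, 2 g vs 0 g: (1-3) - (0-0) = -2b; -3b.
- Dose main effect, 4 g vs 0 g: (0+0)/2 - (3+0)/2 = -1.5b; -2b.
- Direct 2 g capsules vs 2 g tablets: 1 - 0 = +1b in both versions.
- Direct 4 g capsules vs 4 g tablets: 0.
- 4 g capsules vs water: 0.

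The form-by-dose bias at 4 g is simply minus the whole placebo-versus-water difference, so that result does not need linearity.

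**3. Can the model adjust for inulin?** The dose × form model has six cells and rank 6. Adding an inulin term gives seven columns and still rank 6, so the term cannot be estimated. It becomes estimable (rank 5 of 5) only if form-by-dose is assumed to be zero, which assumes away part of the formulation question.

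**4. Effect on the primary endpoint (illustration).** Suppose 4 g capsules truly lower the AUC by 33% against water, and the inulin placebo lowers it by a fraction i. The documents give no value for i; these are assumptions. Apparent reduction against placebo capsules = 1 - 0.67/(1 - i):

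- i = 0.05: 1 - 0.67/0.95 = 29.5%
- i = 0.10: 1 - 0.67/0.90 = 25.6%
- i = -0.05 (inulin raises the AUC): 1 - 0.67/1.05 = 36.2%

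Tablets with the same activity would read 33% against water. At i = 0.05 the two blocks would differ by 33 - 29.5 = 3.5 points with no formulation difference. On the same assumption and linearity, the direct 2 g comparison would be shifted by only 5/3 = 1.7 or 5/4 = 1.25 points of the water AUC, and the 4 g comparison not at all.

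**5. Precision of placebo capsules versus water.** The plan's own figure is 80% power for a 17% difference at n=20 with a 25% CV. Taking 25% as the SD of the paired difference, a noncentral t calculation gives 82.2% power at 17% and an 80% detectable difference of 16.5%, which agrees after rounding. With that SD the 95% CI half-width is 2.093 × 25/√20 = 11.7 points. If 25% is instead the CV of a single value, the SD of a difference is 25 × √2 = 35.4 and the half-width is 2.093 × 35.4/√20, about 16.5 points.

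**The case against.** Much can be said for the plan.

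- **Clean comparisons exist.** A reader might infer that no capsule-versus-tablet comparison can be separated from inulin. The documents do not support that. Neither 4 g arm contains placebo capsules, and the 2 g arms differ by 1 g of inulin. This stands, and it limits the point to the factorial terms and to reductions taken against each block's own zero arm.
- **The zero arms are not declared to be pooled.** Water is listed as a separate treatment, and the full model gives every cell its own mean. That is right; only the dose main effect averages the two. The remaining issue is what the form and interaction terms mean when the 0 g cells are included.
- **Tukey's test could compare placebo with water.** It could, but only after a significant overall test. The text does not say which means are compared, and no interval is promised. A non-significant result would not show that the placebo is inert.
- **The harm has no figure in the documents.** True. The 5% and 10% values are assumptions, and crossing the 33% line at 5% supposes a true effect sitting at that line.
- **The contrast is too imprecise to settle a 5% effect.** Also true. It also mixes inulin with capsule, block and open-label effects. Reporting it describes the uncertainty and does not remove it.

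**Conclusion.** The point holds in a limited form. By the plan's own capsule counts, the form main effect carries +1.33b or +1.67b of inulin effect, and the form-by-dose term at 4 g carries -3b or -4b. The dose main effect averages two different zero arms. The primary % reduction has two possible references and names neither. More subjects would not remove this bias.

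The documents do not show that inulin alters glucose or insulin, so neither the size nor the sign of the bias is known. Nor do they support the reading that the formulation question is unanswerable: the trial already collects same-dose active comparisons, one of them free of inulin. The conclusion rests on inulin-free tablets and, for the per-gram figures, on a linear effect. It is a specification gap that can be closed without new data.

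**What to change.** Amend Statistical Analysis before unblinding:

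1. Base the formulation conclusion on 2 g capsules versus 2 g tablets and 4 g capsules versus 4 g tablets, noting that only the latter is free of inulin. Do not base it on a form main effect or interaction that includes the 0 g cells.
2. Name the primary reference arm for % reduction, and report capsule reductions against both placebo capsules and water alone.
3. Keep the two 0 g treatments as separate levels, and report placebo capsules versus water with a 95% CI whether or not the overall test is significant.

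Separately, reconcile the number of placebo capsules in the zero arm (12 in Treatments, 16 under Table 1), since it sets the inulin load.

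The cost is a few sentences and no new data or product; a different placebo filler is not proposed. The downsides should be stated in the report. The placebo-versus-water interval will be about ±12 to ±17 points at n=20, and it cannot prove inulin inert. Capsule comparisons against water or tablets cross the blinded and open-label blocks.
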